# 6 Study Methods

#### 6.1 General Study Design and Plan

This is a single-arm, prospective, non-randomized, multi-center, open-label, pivotal study. The study intends to enroll a maximum of 42 subjects within the United States. For each treatment location (pulmonary artery or aortic vascular), a minimum of 10 patients will be treated. These subjects will be enrolled at up to 8 US investigational sites, with the possibility of additional Japanese and/or European Union sites pending the appropriate regulatory approval. A minimum of 50% of patients must be treated at sites within the Unites States. As there have been no stent related design changes as a result of the EFS implants, the initial 10 patients will be included in the 36-42 patients.

# 6.2 Inclusion-Exclusion Criteria and General Study Population

The study population will be comprised of patients with a clinically relevant pulmonary artery or aortic vascular stenosis who are indicated for treatment. For each treatment location (pulmonary artery or aortic vascular), a minimum of 10 patients will be treated.

# **Inclusion Criteria**

Candidates must meet **all** of the following inclusion criteria:

- 1. The subject's legally authorized representative has been informed of the nature of the clinical investigation, agrees to its provisions, and has provided written informed consent.\*
- 2. Requiring treatment\* of:
  - a. Native, acquired, or recurrent aortic coarctation, and/or
  - b. Native, acquired, or recurrent pulmonary artery stenosis

\*As defined by the patient's medical team

- 3. Patency of at least one femoral, jugular vessel, or both carotid arteries able to accommodate the delivery system
- 4. Adjacent vessel to stenosis measuring > or equal to 4 mm

\*This clinical investigation is enrolling neonates, infants, and young children. All local laws and governing Institutional Review Board (IRB) requirements will be followed for obtaining informed consent.

# **Exclusion Criteria**

Candidates will be excluded from the clinical investigation if any of the following are present:

- 1. Active bloodstream infection requiring antibiotic therapy within 7 days prior to stent implantation
- 2. History of or active endocarditis (active treatment with antibiotics) within 180 days prior to stent implantation
- 3. Aortic or pulmonary artery aneurysm in the location targeted for treatment
- 4. Body weight of < 1.5 kg
- 5. Anatomic location of lesion judged by the investigator to not lend to the safe placement of a stent
- 6. Target vessels larger or smaller than the Minima System balloon size ranges
- 7. Currently participating in an investigational drug study or another device study
- 8. Known genetic syndrome known to be associated with vasculopathies such as but not limited to Williams syndrome, Loeys-Dietz syndrome, etc
- 9. Clinical scenario requiring that more than one vessel needs stent implantation at the time of trial procedure.
- 10. Major or progressive non-cardiac disease resulting in a life expectancy of less than six months
- 11. Known hypersensitivity to aspirin or heparin and cannot be treated with other antiplatelet and/or antithrombotic medications
- 12. Known hypersensitivity to cobalt-chromium or contrast media that cannot be adequately pre-medicated

#### **Inclusion Criteria for Re-dilation**

Candidates must meet one or more of the following inclusion criteria:

Development of an increase in the pressure gradient across the stent and/or stent lumen diameter less than the nominal adjacent vessel diameter, as defined as:

- 1. Peak Doppler echo gradient  $\geq$  30 mmHg and/or a mean Doppler gradient  $\geq$ 20 mmHg across the stented vessel
- 2. Stented lumen diameter is  $\leq$  75% of adjacent native vessel

### **Exclusion Criteria for Re-dilation**

Candidates must not have any of the following:

- 1. Evidence of significant vessel wall damage (e.g., aneurysm, dissection) in the area of planned re-dilation
- 2. Stent deformity or loss of structural integrity judged by the investigator to not lend to the safe re-dilation of the stent
- 3. Access site or patient vasculature judged by the investigator to not lend to the safe re-catheterization using a balloon catheter approved for the stent location..

#### 6.3 Study Assessments

Activity	Screening	Procedure	Post-Procedure	1 Month (±7days)	3 Months (±7days)	6 Months ±14 days)	12 Months (±30days)	Annually Years 2-5 (±45days)
Informed consent & HIPAA authorization	Х							
Inclusion/exclusion criteria assessment	Х							
Demographics	Х							
Medical history	Х							
Physical exam & vital signs	Х		X	X	X	X	X	X
WBC, Hgb, Hct, platelets	$X^1$							
Serum creatinine	$X^1$							
INR (if taking Warfarin)	Х							
Chest X-ray	Х		X	X	X	X		
Transthoracic echocardiogram	Х		X	X	X	X	X	Х
Concomitant medications	Х	X	X	X	X	X	X	X
Minima stent implantation		X						
Pre-and Post-implantation angiography and hemodynamic assessments (within procedure)		X						
Adverse events / Device deficiencies 		X	X	X	X	X	X	X
Concomitant procedures 	Х		X	X	X	X		
CT angiography						X 		

To reduce unnecessary blood draws from patients, blood work may be performed after successful completion of all other screening activities / in the catheterization lab prior to device introduction into the bloodstream.

 All AEs collected for 12 months post-transplant; after 12 months, see Section 8.2 for select AE reporting.

 See Section 8.8 for reporting of select concomitant medications/procedures.

 Catheter-based angiography can be performed in place of CT if clinically appropriate.

The table below defines the analysis time windows that correspond to the targeted visit time frame.

Visit (target day)	Lower bound (days)	Upper bound (days)
Month 1 (30)	2	60
Month 3 (90)	61	135
Month 6 (180)	136	270
Month 12 (360)	271	374

Analysis Time Windows

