#### **Missed window**

For missed data collection, confidence intervals, standard deviations and other calculations dependent on sample size will be calculated using the reduced sample size, unless noted otherwise in the resolution of the protocol deviation.

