#### **Duplicate Measurements Within Window**

In the event multiple measurements are made within window (due to an unscheduled visit or other event), the implanting physician for the subject is responsible for determining which visit conducted is the scheduled visit. The unscheduled visit will still be documented within the database using an unscheduled visit form; however, the datapoints will not be used in follow-up calculations unless instructed to do so as part of a resolution of a protocol deviation.

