# 8 General Analysis Considerations

#### 8.1 Timing of Analyses

The first analysis will be performed when a minimum of 10 subjects have completed the 6 month visit.

Primary analysis and submission of available data will be completed after all patients have completed their 6 month follow-up visits.

Subsequent analysis will be completed annually through 5 years.

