# 9 Summary of Study Data

All continuous variables will be summarized using the following descriptive statistics: n (non-missing sample size), mean, standard deviation, median, maximum and minimum. The frequency and percentages (based on the non-missing sample size) of observed levels will be reported for all categorical measures. All summary tables will be structured with a column for treatment and will be annotated with the total population size relevant to that table, including any missing observations.

Only deviations from the general overview will be noted in the subsequent sub-sections within section 9.

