#### 9.1 Subject Disposition

The number of patients completing each visit from the schedule of assessments will be reported along with the reason for loss (screen failure, death, loss to follow-up, etc).

The summary statistics will be produced in accordance with section 9.

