# **10 Efficacy Analyses**

### **10.1 Primary Efficacy Analysis**

The primary efficacy endpoint will be assessed as the rate of clinical success, with the performance goal defined as a clinical success rate of greater than 77%.

Clinical success is defined as:

- Stenosis relief, defined by stent outer diameter  $\geq$  75% of the surrounding vessel immediately after deployment.
- Freedom from open surgical intervention required to treat Minima Stent disfunction through 6 months.
- Maintenance of stented vessel diameter ≥ 50% of post-implant diameter at 6 months; as measured using CT angiography and/or angiography.

The AI patient population will be used to test the study hypothesis. The Clopper-Pearson method will be used to calculate the two-sided 95% confidence limits. If the lower limit of the resulting confidence interval exceeds 77%, then the null hypothesis will be rejected in favor of the alternative. This study hypothesis will be tested without imputation of missing data; however, additional sensitivity analyses will be performed to evaluate the effect of missing data on the study conclusions.

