# **11.3 Adverse Events**

The summary statistics will be produced in accordance with section 9.

The following tables will be generated:

- All-Cause Mortality: A table of all anticipated and unanticipated deaths due to any cause, with number and frequency of such events in each arm/group of the clinical study.
- Serious Adverse Events: A table of all anticipated and unanticipated serious adverse events, grouped by organ system, with number and frequency of such events
- Other (Not Including Serious) Adverse Events: A table of anticipated and unanticipated events (not included in the serious adverse event table) grouped by organ system, with number and frequency of such events.

The number of events as well as the number of patients with each event will be summarized by time interval, The time intervals will be 0 to 30 days, 31-90 days and 91 to 180 days, 180 to 365 and annually through 5 years. The denominator will include all subjects in the AT population with follow-up data during the specific time interval.

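### The Month 12 analysis window stops at day 374, but the schedule allows the visit up to day 390, so on-time visits on days 375–390 belong to no listed window

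*SAP*

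**What the plan says.** SAP section 6.3 contains two tables that bear on visit timing. The schedule of assessments gives each follow-up visit a tolerance: ±7 days at 1 and 3 months, ±14 days at 6 months, ±30 days at 12 months and ±45 days for the annual visits in Years 2–5. The analysis window table follows, introduced by "The table below defines the analysis time windows that correspond to the targeted visit time frame". Its last row is Month 12, with target day 360, lower bound 271 and upper bound 374. It has no rows for Years 2–5.

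Two rules follow the tables. The missed-window rule says that "calculations dependent on sample size will be calculated using the reduced sample size", unless the resolution of a protocol deviation says otherwise. The duplicates rule begins "In the event multiple measurements are made within window" and leaves the implanting physician to decide which visit is the scheduled one.

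Elsewhere, section 9.1 states that "The number of patients completing each visit from the schedule of assessments will be reported", so disposition follows the schedule and not the analysis windows. Section 8.1 plans further analyses every year through 5 years after the primary analysis.

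**The concern.** The analysis windows are said to match the visit time frame, and for Month 12 they do not. A subject seen on day 380 is on time under the schedule and is a completed 12-month visit in the disposition table, yet has no analysis window. A 12-month summary that applies the window table as written would omit that subject. The alternative is for the analyst to adopt an unwritten assignment rule once the data are in hand.

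Physical examination, vital signs, echocardiography and concomitant medications are all scheduled at 12 months. The SAP specifies no particular 12-month table. That such summaries are intended is an inference from three things: a Month 12 window exists, the duplicates rule refers to follow-up calculations, and section 8.1 plans annual analyses. A shortfall would at least be visible, since section 9 requires tables to be "annotated with the total population size relevant to that table, including any missing observations". It would, however, show an on-time visit as missing.

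**Working it through.** **Inputs.** Tolerances come from the schedule of assessments, and target days and bounds from the analysis window table, both in SAP section 6.3.

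**Formulas.** Permitted visit range = target day ± tolerance. Number of permitted days = 2 × tolerance + 1. Uncovered days are permitted days that lie in no listed analysis window.

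| Visit | Target ± tolerance | Permitted range | Analysis window | Upper bound minus last permitted day | Uncovered days |
|---|---|---|---|---|---|
| Month 1 | 30 ± 7 | 23–37 | 2–60 | 60 − 37 = +23 | 0 of 15 |
| Month 3 | 90 ± 7 | 83–97 | 61–135 | 135 − 97 = +38 | 0 of 15 |
| Month 6 | 180 ± 14 | 166–194 | 136–270 | 270 − 194 = +76 | 0 of 29 |
| Month 12 | 360 ± 30 | 330–390 | 271–374 | 374 − 390 = −16 | 16 of 61 |

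For Month 12 the uncovered days are 375–390: 390 − 375 + 1 = 16, and 16/61 = 26.2%.

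**Sensitivity to the day convention.** The table's own target is day 360. If 12 months is instead counted as day 365 (an assumption, although the adverse event intervals in section 11.3 use that boundary: "180 to 365 and annually through 5 years"), the permitted range is 335–395 and the uncovered days are 375–395. That is 21 days, and 21/61 = 34.4%. The gap exists on either convention.

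**Can 374 be reproduced?** The other three upper bounds are exact midpoints between neighbouring targets: (30 + 90)/2 = 60, (90 + 180)/2 = 135 and (180 + 360)/2 = 270. With Year 2 at day 720 (an assumption), the same rule gives (360 + 720)/2 = 540 for Month 12. Target plus tolerance gives 360 + 30 = 390. Neither yields 374. The figure does equal 360 + 14, and 14 days is the Month 6 tolerance. That may be its origin, but this is only an inference.

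**Does another rule catch days 375–390?** No.
- Month 12 is the last row, so no later window picks these days up.
- The missed-window rule is for data that were not collected, and a day-380 visit was collected.
- The duplicates rule chooses between several measurements and does not assign a single late one.
- Nothing in the SAP says that the scheduled visit label overrides the analysis windows.

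**What is not affected.** The imaging component of the primary efficacy endpoint is a comparison with the stated percentage "of post-implant diameter at 6 months; as measured using CT angiography and/or angiography", and the Month 6 window contains its whole visit range. On timing, section 8.1 states: "Primary analysis and submission of available data will be completed after all patients have completed their 6 month follow-up visits". The timed secondary safety endpoints in section 11.2 are at 6 months or at 90 days after re-dilation. Adverse events have their own intervals in section 11.3.

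**The case against.** The strongest objection concerns consequence. No analysis named in the SAP is shown to be harmed: no endpoint is read at Month 12, and the summaries at risk are not specified. That is correct, and it keeps the point minor.

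A second objection is that late visits need not be dropped. Annual analyses run to Year 5 although the window table has no rows beyond Month 12, so later visits must be assigned some other way, perhaps by scheduled visit label. The same method could serve a day-380 visit. This stands in part: omission is certain only for summaries that apply the windows as written. But the SAP states no such alternative for Month 12, and it does give a Month 12 window.

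Third, the duplicates rule does not say whether its window is the visit window or the analysis window. On the first reading, the implanting physician could designate a day-380 visit as the scheduled one. That would apply only where there are several measurements, and it would still leave the visit outside the analysis window.

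Fourth, 26.2% is a share of permitted days and not of visits, and the 34.4% figure replaces the table's own target. Both cautions are right. Neither percentage should be read as expected data loss.

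Fifth, raising one cell leaves the missing Years 2–5 rows open. This is true, but it is a separate gap. The Month 12 contradiction can be corrected without waiting for it.

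**Conclusion.** The concern holds. On the SAP's own day-360 target, 16 of 61 permitted days for the 12-month visit (days 375–390) lie in no listed analysis window, while the other three visits have no uncovered days. The result rests only on the printed target, tolerance and upper bound. The 21-day figure additionally assumes a 365-day year.

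Severity is minor. The exposure is limited to descriptive 12-month by-visit summaries that use the windows. The hypothesis tests, alpha, power and sample size are unaffected, and the documents do not allow an estimate of how many subjects would fall in the gap.

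**What to change.** Reconcile the two tables in SAP section 6.3 by raising the Month 12 upper bound from 374 to at least day 390. Day 395 would also cover a 365-day convention. The scheduled ±30-day tolerance stays as it is.

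If rows for Years 2–5 are added in the same revision, state their target days first and make each row contain its ±45-day visit range on that convention. With Year 2 at day 720 or day 730 (both assumptions), the permitted range starts at 720 − 45 = 675 or 730 − 45 = 685, well clear of day 395.

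The cost is one table cell. Because Month 12 is the last row, a higher bound overlaps no other listed window, moves no visit out of an existing window and changes no endpoint analysis. The correction should be made before 12-month data are summarised.

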#### **Missed window**

For missed data collection, confidence intervals, standard deviations and other calculations dependent on sample size will be calculated using the reduced sample size, unless noted otherwise in the resolution of the protocol deviation.

#### **Duplicate Measurements Within Window**

In the event multiple measurements are made within window (due to an unscheduled visit or other event), the implanting physician for the subject is responsible for determining which visit conducted is the scheduled visit. The unscheduled visit will still be documented within the database using an unscheduled visit form; however, the datapoints will not be used in follow-up calculations unless instructed to do so as part of a resolution of a protocol deviation.

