# **10.2 Secondary Efficacy Analyses**

The secondary efficacy endpoints are as follows:

- Peak-to-peak pressure gradient (ventricle to arterial or arterial to arterial) < 20 mmHg after stent placement, when applicable.
- Successful stent re-dilation (when indicated) at re-catheterization, defined as an increase in the intra stent angiographic luminal diameter of within 2mm of the adjacent native vessel diameter immediately after re-dilation.

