#### 13 Missing Data Considerations

The hypothesis tests for the primary endpoints will be performed without imputation of missing data. The incidence of missing data is expected to be low and all efforts will be made to collect all required data points in the study. Should there be missing data for either primary endpoint, then sensitivity analyses will be performed to evaluate the potential effect of the missing data on the study conclusions. If the study conclusions are upheld using a worst-case scenario imputation approach, then no further missing data analyses will be required. The worst-case scenario approach would treat all missing data points as failures for the endpoint.

If the results are not upheld with the worst-case scenario approach, then two further analyses will be performed.

- 1) A tipping point analysis: missing data are imputed over the range of possible scenarios, from imputing all as successes to all as failures, in order to determine at what point the hypothesis is no longer met.
- 2) Multiple Imputation: A multiple imputation analysis will be performed using a logistic regression model. Variables in the model will include:
  - a. Lesion Location (Aortic, Pulmonary)
  - b. Age
  - c. Weight

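### The implanting physician picks, with no stated criterion, which in-window visit counts; this can reach the 6-month diameter component of primary efficacy, and no planned sensitivity analysis tests it (minor)

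*SAP*

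**What the plan says.** SAP 6.3, under Duplicate Measurements Within Window, covers the case of several measurements in one window. There, "the implanting physician for the subject is responsible for determining which visit conducted is the scheduled visit". The remaining visit is recorded as unscheduled, and "the datapoints will not be used in follow-up calculations unless instructed to do so as part of a resolution of a protocol deviation". The SAP gives no basis for the choice, such as closest to target, first, last or worst. It does not say whether the images have been read when the choice is made.

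The rule names no endpoint. It follows the table of analysis time windows, where Month 6 (target day 180) runs from day 136 to day 270. The assessment schedule in the same section gives a visit window of ±14 days for Month 6.

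The third component of clinical success (SAP 10.1) is a stented vessel diameter of at least 50% "of post-implant diameter at 6 months; as measured using CT angiography and/or angiography". CT angiography is scheduled once, at 6 months, and a footnote adds: "Catheter-based angiography can be performed in place of CT if clinically appropriate".

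On design, SAP 6.1 states: "This is a single-arm, prospective, non-randomized, multi-center, open-label, pivotal study". On robustness, SAP 10.1 promises that "additional sensitivity analyses will be performed to evaluate the effect of missing data on the study conclusions", and SAP 13 sets the trigger: "Should there be missing data for either primary endpoint, then sensitivity analyses will be performed".

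**The concern.** The third component is the only imaging measure of durability in the primary efficacy endpoint. If a subject has two qualifying images at separate visits in the Month 6 window, the physician who placed the stent decides which one enters the test, and may already know both results. The choice need not be deliberate to be biased. It is enough that the selection can depend on the outcome and that no rule prevents this.

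The planned analyses would not reveal it. A subject with two readings has no missing value, so the worst-case, tipping-point and multiple-imputation analyses in SAP 13 do not address that subject. The study report could not show whether the efficacy result depended on which visit was labelled as scheduled.

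The first component (diameter immediately after deployment) and the second (freedom from open surgery, an event) are not affected.

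**Working it through.** **Inputs.** Performance goal 77%, success if the lower limit of the two-sided 95% Clopper-Pearson interval exceeds it (SAP 10.1). Planned success rate 97%, minimum 36 subjects, maximum 42 US subjects (SAP 7). The documents give no frequency for second in-window images.

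**The plan's own figure.** Power by the normal approximation is Φ((|p1−p0|√n − 1.96√(p0(1−p0))) / √(p1(1−p1))). At n = 36 it is 0.986 for efficacy and 0.914 for safety, product 0.902. The SAP table gives 0.99, 0.91 and 0.90, so the design inputs reproduce.

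**Pass mark.** The lower limit for x successes in n is the 2.5% quantile of Beta(x, n−x+1).

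| n | successes | lower limit | result |
|---|---|---|---|
| 36 | 32 | 73.9% | fail |
| 36 | 33 | 77.5% | pass |
| 42 | 37 | 74.4% | fail |
| 42 | 38 | 77.4% | pass |

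**Where one subject matters.** One failure re-scored as a success changes the result only if the count is exactly one below the pass mark.

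- n = 36: P(X = 32) = C(36,4) × p^32 × (1−p)^4, which is 3.8% at p = 0.77 and 1.8% at p = 0.97.
- n = 42: P(X = 37) = C(42,5) × p^37 × (1−p)^5, which is 3.5% at p = 0.77 and 0.7% at p = 0.97.

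These are probabilities of standing at the boundary. For the choice to change the result, that trial must also contain a subject with two in-window images that fall on opposite sides of 50% of the post-implant diameter.

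**Illustration at a true rate of 77%.** With no re-scoring, the probability of passing efficacy wrongly is P(X ≥ 33) = 2.12% at n = 36 and P(X ≥ 38) = 2.20% at n = 42. Let f be the share of failures due to the third component and r the share of those re-scored as successes. Both are assumptions with no source in the documents. The success rate becomes 0.77 + 0.23·f·r.

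| r | n = 36, f = 1/3 | n = 36, f = 1/2 | n = 42, f = 1/3 | n = 42, f = 1/2 |
|---|---|---|---|---|
| 0.05 | 2.39% | 2.53% | 2.50% | 2.67% |
| 0.10 | 2.69% | 3.02% | 2.85% | 3.23% |
| 0.25 | 3.81% | 5.04% | 4.14% | 5.58% |

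The last row with f = 1/2 implies 0.23 × 36 × 0.5 × 0.25 = 1.04 re-scored subjects per trial on average (1.21 at n = 42). The model lets every re-scoring go in the favourable direction. The figures are for efficacy alone; the study passes only if safety also rejects its null hypothesis.

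**The case against.** The rule governs visits, not images, and is general data management. It matters only if a second CT or catheter angiogram exists, at a separate visit, in the same window, and the two readings straddle the 50% threshold. Nothing in the documents suggests that this is common. All of this stands, and it limits the size of the point.

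The term for the window is also ambiguous. ±14 days around day 180 is days 166 to 194 (29 days); the analysis window is days 136 to 270 (135 days). Under the narrower reading a second image would be rarer. That stands too, and is itself worth one clarifying phrase.

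Unselected data stay in the database and can be brought in through a deviation resolution, so the choice can be audited. This helps, but it works case by case without a criterion and is not a planned analysis. Only the protocol synopsis is available, so a rule on image reading or visit labelling elsewhere cannot be excluded.

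Two stronger readings are tempting.

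- **A reader might infer that type I error is materially inflated, to about 5%.** The documents do not support that. It needs about one favourable re-scoring per trial, and at 5% re-scoring the figure stays at 2.4% to 2.7%, close to the nominal 2.5%.
- **A reader might infer that re-dilated subjects are being passed as successes through this rule and should count as failures.** Images before and after re-dilation in one catheterization belong to one visit, so the rule does not choose between them. The SAP introduction presents re-dilation over time as the expected response to growth, and SAP 10.2 gives it a secondary endpoint: "Successful stent re-dilation (when indicated) at re-catheterization". How re-dilation is scored is a separate matter. It is relevant here only as one way in which a second angiogram could arise, and that still requires another image at a different visit in the window.

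**Conclusion.** The point holds as a minor one. The SAP states an outcome-permissive selection rule in an open-label trial, and no planned analysis tests it. That much is on the page and rests on no assumption.

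The likely effect is small. A single favourable re-scoring matters only at exactly 32/36 or 37/42, and at the planned 97% those counts arise in 1.8% and 0.7% of trials, before allowing for how seldom a suitable duplicate would exist. These figures assume 36 or 42 evaluable subjects and independent outcomes. The inflated error rates are illustrations only, since the frequency of duplicates is unknown. The documents do not show that any bias will occur.

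**What to change.** In SAP 6.3:

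1. State that the window in the duplicate rule is the analysis window (days 136 to 270 for Month 6).
2. For the primary endpoint, replace the physician's choice with a rule that does not depend on the result. For example: the CT or angiographic measurement closest to day 180, the earlier one if two are equally close.
3. Report how many subjects have more than one in-window image, and whether any of those images was taken after re-dilation. The second count is needed because a date-based rule can itself select a post-re-dilation image.
4. Repeat the primary efficacy analysis with the non-selected, or the worst, in-window image.

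The endpoint definition and the scoring of re-dilation stay as they are. The cost is a sentence or two, a short count and one small sensitivity analysis, with no added visit, scan or subject. The downside for the sponsor is that the success rate may come out slightly lower.
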